#### Discomfort Glare (change in palpebral fissure height (mm))

Glare discomfort (GD) will be evaluated by squint response of the extraocular muscles and by a subjective questionnaire regarding the patients' comfort. Squint response will be captured by using a high-resolution camera for each subject eye. The resultant videos will then be analyzed as still frames. Squint response will be quantified as the calculated ratio of the height of the palpebral fissure under normal light conditions compared to maximal squint produced during the Photostress exposure. GD will be analyzed in the same manner as described for PSRT.

Comparisons between lenses will be carried out using 2-sided 95% confidence intervals constructed for the least-square mean (LSM) difference (Test – Control). Statistically significantly higher differences of the Test lens relative to the Control lens will be concluded if the lower limit of the 95% confidence interval is above 0. If the interaction between lense type and age is significant then comparisons between lenses will be made within age group.

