2	Heterochromatic Contrast Threshold (HCT)	Chromatic contrast will be measured as thresholds to a variable wavelength central target presented on a short-wave (460 nm) sky-light background. This aspect of the testing is mostly exploratory to see how the contacts influence chromatic contrast. The relation to filtering is very strong as long as there is differential filtering between the target and the background.	
		Stimulus size Stimulus size	

Page 39 of 117

	Psychophysical Testing A: Photostress / Glare / Chromatic Contrast			
3	Photostress Recovery (PR)	To measure PR time, participants are exposed to the same target used in each of the other visual function tests. Once the participant is comfortably viewing the target, the experimenter will cover the target with a bright, bleaching light. Exposure to the light will cause participants to momentarily lose sight of the target, which will be covered by an afterimage. As the afterimage fades, participants will gradually be able to re-gain sight of the target. PR time will be recorded as the time it takes following exposure to the bleaching light to regain sight of the target.		
4	Glare Discomfort (GDc)	
 
Glare discomfort (GDc) will be quantified using the squint response and a questionnaire. The discomfort that accompanies exposure to light in excess of an individual's adaptive state is accompanied by contraction of the extraocular muscles (squint). The squint response has been shown to be a valid objective indicator of glare discomfort. This procedure was described by Gowrisankaran. Degree of squint is calculated as the ratio of the height of the palpebral fissure under normal lighting conditions compared to maximal squint produced during the photostress exposure. A high-resolution camera (AmScope MU300 digital camera; Irvine, CA) will be used and calibrated against a spatial standard before the start of each day of testing. The resultant videos will be analyzed as still frames using AmScope measurement software (Irvine, CA). To determine subjective ratings of GDc, subjects will be asked to rate the degree of discomfort of the photostressor using a single-item questionnaire OD and OS:
 
How bothersome was the glare that you just experienced? Subjects will have the following response options: Extremely bothersome, Very bothersome, Somewhat bothersome, A little bothersome, Not at all bothersome.
 
		

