## 14.2. Sample Size Justification

The plan is to enroll a maximum of 66 subjects with a minimum target of 60 subjects to complete. The sample size was chosen by the study responsible clinician and was not based on any empirical power calculation. Furthermore, a power calculation cannot be provided for any of the primary endpoints because no historical data is available. This data from this study will be utilized in the sample size calculations for any additional follow-up studies.

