## 14.4. Level of Statistical Significance

Each primary and secondary hypothesis will be tested individually using a type I error rate of 5%.

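### Discomfort glare is worded as resting lid height over squint height; if that is the scale analysed, dividing by squint height loses precision, so define one outcome that does not

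*Combined protocol and SAP*

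**What the plan says.** Section 7.2 (Psychophysical Testing A, step 4) states: "Degree of squint is calculated as the ratio of the height of the palpebral fissure under normal lighting conditions compared to maximal squint". Section 14.6 repeats it: "Squint response will be quantified as the calculated ratio of the height of the palpebral fissure under normal light conditions compared to maximal squint". In both places the maximal squint is the one produced by the photostress exposure. The subheading in 14.6 describes something else, a difference in millimetres: "Discomfort Glare (change in palpebral fissure height (mm" (closing brackets omitted).

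Section 14.6 sends the analysis to the photostress-recovery model. That is a linear mixed model with sequence, lens type, age group, dominant eye and lens-by-age interaction. It has no transformation and no term for resting height. "Comparisons between lenses will be carried out using 2-sided 95% confidence intervals" on least-squares means, and "Statistically significantly higher differences of the Test lens relative to the Control lens will be concluded if the lower limit" lies above 0. Secondary hypothesis 3 in Section 2.3 expects the Test lens to be lower on eyelid squinting.

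Section 14.4: "Each primary and secondary hypothesis will be tested individually using a type I error rate of 5"%. Section 14.2: "The plan is to enroll a maximum of 66 subjects with a minimum target of 60 subjects to complete" and "The sample size was chosen by the study responsible clinician and was not based on any empirical power calculation". Section 15.1 has the discomfort-glare value worked out at the site and entered there. The heterochromatic contrast paragraph in 14.6 takes its analysis by reference from discomfort glare.

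**The concern.** If the outcome is resting height divided by maximal-squint height, equal lid movements do not count equally. A subject who nearly closes the lids produces a large and unstable ratio, and an error of a fraction of a millimetre in that eye can outweigh a consistent difference in many mild squinters. The exposure is a bleaching light and the measurement is the maximal squint, so small denominators are plausible. A linear model compared on means gives such values full weight. At stake is the power of one secondary hypothesis in a trial whose size was not set by a power calculation.

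**Working it through.** **Inputs from the documents.** 60 completers, hence 60 eye pairs (14.2); two-sided 5% per hypothesis (14.4); mean comparison without transformation or resting-height term (14.6). There is no SD, effect size or lid-closure frequency for squint, so the plan has no figure to reproduce.

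**Step 1: the scale itself, with H = resting height and S = squint height.** Take H = 10 mm for illustration.
- H/S, 6 to 5 mm: 10/5 - 10/6 = 2.00 - 1.67 = 0.33.
- H/S, 2 to 1 mm: 10/1 - 10/2 = 10 - 5 = 5, which is 15 times as much for the same 1 mm.
- S/H: 0.6 to 0.5 and 0.2 to 0.1, both a change of 0.1. In mm, both are 1.
- The slope of H/S in S is -H/S². It is 10/36 = 0.28 per mm at S = 6 and 10 per mm at S = 1, so a given measurement error is magnified 36-fold.

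This step needs only the illustrative heights.

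**Step 2: power when squint varies in points of resting height.** Assumed: resting height 10 mm (SD 1.2), mean squint 40-60% of resting, SD between subjects 15-20 points, noise 6 points per exposure, smallest readable opening 0.5-1 mm, true benefit 3 points (0.03 × 10 = 0.3 mm).
- Benchmark for S/H, ignoring measurement error: SD of the between-eye difference = 6√2 = 8.49 points; expected t = 3/8.49 × √60 = 2.74; power about Φ(2.74 - 2.00) = 0.77.
- Simulated power: rest/squint 0.30-0.55, mm change 0.61-0.64, adjusted squint height 0.73-0.74. Rest/squint has 31-64% of the efficiency of the adjusted analysis, a gain of 1/0.64 = 1.6 to 1/0.31 = 3.2.
- A further run at 6 points of noise: rest/squint 0.32-0.70, adjusted 0.66-0.75, squint/rest 0.67-0.77.

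**Step 3: a different set of assumptions.** Resting height 10 mm, between-eye resting SD 0.4 mm, measurement error 0.2 mm, 3,000 simulated trials per row. Efficiency gain = (mean t adjusted / mean t rest/squint)².

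| Typical S/H, spread, lens effect | Smallest S (mm) | Skewness of H/S | Variance share of top 3 of 60 | Mean t: H/S, adjusted | Power: H/S, adjusted, S/H | Gain |
|---|---|---|---|---|---|---|
| 0.7, moderate, additive | 0.3 | 1.0 | 0.35 | 2.40, 2.57 | 0.67, 0.71, 0.71 | 1.15 |
| 0.6, moderate, proportional | 0.3 | 3.1 | 0.60 | 1.72, 2.62 | 0.51, 0.74, 0.75 | 2.32 |
| 0.5, wide, additive | 0.3 | 3.7 | 0.63 | 1.37, 2.79 | 0.49, 0.77, 0.78 | 4.12 |
| 0.25, wide, proportional | 0.1 | 4.3 | 0.76 | 1.27, 2.59 | 0.27, 0.73, 0.74 | 4.15 |
| 0.25, wide, proportional | 1.0 | 0.8 | 0.34 | 2.35, 2.52 | 0.63, 0.69, 0.71 | 1.14 |

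For the second row, (2.62/1.72)² = 2.32. Across all settings run, the gain over rest/squint was about 1.1 to 4.2. The efficiency of the adjusted analysis relative to squint/rest was 0.95-1.03, so there was no gain over that ratio.

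**The case against.** The strongest reply is that the outcome may not be rest/squint at all. Saying that one height is compared to another does not fix numerator and denominator. The subheading speaks of a change in mm. The success rule rewards a higher value, whereas under rest/squint a higher value means more squinting, against secondary hypothesis 3. The rule fits squint/rest, where there is no small denominator and nothing to gain. This stands, and it makes the precision loss conditional.

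A reader might also infer that adjusting for resting height is what buys the precision. The calculations do not support that: most of the gain comes from leaving the reciprocal. Unadjusted squint height had power 0.75 against 0.76 adjusted in the central case. The covariate mattered where closure varied little (0.52 against 0.64) or where the between-eye resting SD was 1.0 mm (0.63 against 0.74). A log ratio recovers much of the loss on a relative scale; the efficiency of the adjusted analysis relative to it was about 0.9-1.35.

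Two technical limits also stand. The step 2 calculation for adjusted height regressed the between-eye difference in squint height on that in resting height. One raw covariate in the mixed model could mix within- and between-subject slopes, and that model was not simulated. Resting height is also measured after lens assignment, but every ratio or change score shares that feature.

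**Conclusion.** Sections 7.2 and 14.6, read literally, choose a scale that was less precise than adjusted squint height in every setting run. Power is about 0.3-0.7 against about 0.65-0.75 under the step 2 assumptions. The efficiency gain is about 1.1-fold when closure varies little and 3-fold or more when some lids nearly close. The arithmetic of the reciprocal is certain. The size of the loss is not, because every SD, effect and closure rate is assumed. If squint/rest was meant, there is no loss.

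A reader might infer that a few nearly closed lids will dominate the result and that a real benefit will probably be missed. The documents do not support that: they give no lid-closure data, and rest/squint power reaches 0.70 in some settings. Nor would the change rescue a noisy measurement. At 10 points of noise the expected t is 3/(10√2) × √60 = 1.64, and simulated power for the adjusted analysis is only 0.33-0.37.

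What holds without any assumption is that the text, the subheading and the success rule do not describe one scale, and they must be reconciled. This concerns one of four secondary hypotheses; the primary conclusions are unaffected.

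**What to change.** In Sections 7.2 and 14.6, define one discomfort-glare outcome that does not divide by squint height, and make the subheading match. Either of these will do:

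- palpebral fissure height in mm at maximal squint, with that eye's resting height as a covariate in the mixed model, preferably split into the subject's mean and the eye's deviation from it; or
- the ratio squint height / resting height, which keeps a relative scale and needs no covariate.

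Under both, a higher value means less squinting, so the existing rule (lower confidence limit above 0) agrees with secondary hypothesis 3. Report rest/squint descriptively only. State when the resting height is taken. Record both heights for each eye in the EDC, because Section 15.1 as written may capture only the calculated value. If the covariate option is chosen, state that it does not pass to heterochromatic contrast through the cross-reference in 14.6.

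The cost is SAP and procedure wording, a small data-capture change, and a change of scale (an absolute effect in mm if squint height is used). The heights already have to be measured from the videos.

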#### Heterochromatic Contrast Threshold (HCT)

Heterochromatic contrast thresholds will be evaluated using a variable wavelength central target presented on a short-wave (460nm) sky-light background and will be quantified by the amount of light absorbed by the macular.

HCT will be analyzed and tested in the same manner as GD.

## 14.7. Other Exploratory Analyses

In vivo light transmission and slit lamp findings will be descriptively summarized for each lens type.

## 14.8. Interim Analysis

There will not be an interim analysis conducted on this study.

## 14.9. Procedure for Handling Missing Data and Drop-Outs

Missing or spurious values will not be imputed. The count of missing values will be included in the summary tables and listings.

Subject dropout is expected to be one of the main reasons of missing data in this clinical trial. Past clinical trials don't provide the evidence that subject dropout is systematic or not-atrandom. To evaluate the impact of missing data, sensitivity analysis will be conducted using multiple imputation methods if the proportion of subject dropout is greater than the 15%. The SAS/STAT procedures PROC MI and PROC MIANALYZE will be utilized with a parametric regression method used to make at least 10 imputations.

# 14.10. Procedure for Reporting Deviations from Statistical Plan

The analysis will be conducted according to that specified in above sections. There are no known reasons for which it is planned to deviate from these analysis methods. If for any reason a change is made, the change will be documented in the study report along with a justification for the change.

# 15. DATA HANDLING AND RECORD KEEPING/ARCHIVING

## 15.1. Electronic Case Report Form/Data Collection

The data for this study will be captured on electronic case report forms (eCRFs) using an EDC system (Bioclinica). An authorized data originator will enter study data into the eCRFs using the EDC system. Data collected on equipment that is not captured in EDC will be formatted to the specification of the JJVC database manager and sent to JJVC for analysis.

The follow data testing/measurements will be calculated and entered into the EDC at the study site.

- Light Scattering
- Starburst
- Halos
- Photostress Recovery Time
- Disability Glare Threshold
- Discomfort Glare
- Heterochromatic Contrast Threshold

The clinical data will be recorded on dedicated eCRFs specifically designed to match the study procedures for each visit. Once completed, the eCRFs will be reviewed for accuracy and completeness and signed by the Investigator. The sponsor or sponsor's representatives will be authorized to gain access to the subject recordation for the purposes of monitoring and auditing the study.

Edit checks, electronic queries, and audit trails are built into the system to ensure accurate and complete data collection. Data will be transmitted from the clinical site to a secure central database as forms are completed or updated, ensuring information accuracy, security, and confidentiality. After the final database lock, the Investigator will be provided with Individual Patient Profiles (IPP) including the full audit trail on electronic media in PDF format for all of the study data. The IPP must be retained in the study files as a certified copy of the source data for the study.

The content and structure of the eCRFs are compliant with ISO14155:2011.

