## 5.2. Masking

This is a subject-masked study. Masking will be used to reduce potential bias. Subjects will be unaware of the identity of the investigational product. Investigators and clinical site personnel involved in the data collection will not be masked as to the identity of the investigational product. Although the subjects will not be aware of which study lens is going on which eye, the dynamic nature of the test lens during the assessments may give the identity.

Under normal circumstances, the mask should not be broken until all subjects have completed the study and the database is finalized. Otherwise, the mask should be broken only if specific emergency treatment/course of action would be dictated by knowing the treatment status of the subject. In such cases, the Investigator may, in an emergency, contact the medical monitor. In the event the mask is broken, the Sponsor must be informed as soon as possible. The date, time, and reason for the unmasking must be documented in the subject record. The Investigator is also advised not to reveal the study treatment assignment to the clinical site or Sponsor personnel.

Subjects who have had their treatment assignment unmasked are expected to return for all remaining scheduled evaluations. Subjects who are discontinued will be replaced.

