#### Investigational contact lenses

The investigational lenses will be tested with an additional UV/HEV light source as one of the test conditions. "Activation" will be achieved using an ultraviolet activator consisting of LEDs waveband 365-400 nm that combines with the primary optical path of the system, after the final lens of the optical system (see Figure 7). The spectral output of the ultraviolet LEDs is given in Appendix G. The ultra-violet LEDs will be used, at a low constant rate, while the visual measures (halos, etc.) are being collected. The overall energy at the plane of the eye is 64  $\mu$ w/cm2 (measured using the ILT 950, the graph in Appendix G is the light source at the energy we plan to use during the measurement). As a comparison, the UV activator emits 0.07 mw/cm2 whereas mid-day sunlight measured 11 mw/cm2 using the same instrument (1:00 PM, partially cloudy day, September 18, 2017, Athens, GA using a UVA light meter: General UV254SD).

JJVC CONFIDENTIAL

JJVC CONFIDENTIAL

	Psychometric Testing B: Dysphotopsia Evaluation			
	The psychophysical tests described in Steps 1-3 below may occur in any order. All three tests will perfomed twice: once with an UV/HEV activating light source and once with no activating light source. The order of light source testing will be randomized.			
Step	Procedure	Details		
1	Two-point Light Spread Function	These thresholds are defined as the minimum distance that two points of light are completely distinct. An ascending and a descending method of limits will be used. This measurement takes about 10-15 minutes. Record values OD and OS, in mm (2 decimal places).		
2	Starburst	This is defined as the diameter of the light's lateral spread. Subjects will have the nature of starbursts explained using visual aids prior to the experiment. The investigator will adjust a calibrated custom-made micrometer (two sides with reverse threading) to spread two posts out from a central mid-point. Those posts will be used to define the outer boundaries of the starburst image. Ascending and descending methods of limits would be used based on subject feedback. This measurement takes about 10-15		

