		Calipers are adjusted until the inner edges are just touching the edges of the starburst pattern. minutes. Record values OD and OS, in mm (2 decimal places). Subjects will respond to a single-item post- starburst questionnaire OD and OS: • How severe / intense was the starburst that you experienced? Subjects will have the following response options: Severe, moderate, mild, not at all.		

	Psychometric Testing B: Dysphotopsia Evaluation				
	The psychophysical tests described in Steps 1-3 below may occur in any order. All three tests will perfomed twice: once with an UV/HEV activating light source and once with no activating light source. The order of light source testing will be randomized.				
Step	Procedure	Details			
3	Halos	Subjects will have the nature of halos explained using visual aids prior to the experiment. The halo measurement will utilize the same light source as the starburst and two- point measures to produce the halo. The same calibrated micrometer from the starburst test will be used to define the outer edges of the halo image (investigator adjusting based on subject feedback). Ascending and descending methods of limits will be used. This measurement takes about 10-15 minutes. Record values OD and OS, in mm (2 decimal places). Subjects will respond to a single-item post-halo questionnaire OD and OS:			
		• How severe / intense was the halo that you experienced? Subjects will have the following response options: Severe, moderate, mild, not at all.			
4	Repeat	The steps above will be repeated but with the alternate light source testing method. The investigator must allow at least 10 minutes to lapse before starting the second round of testing.			

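### For the three primary measures, unmasked site staff turn ascending and descending settings into the endpoint with no fixed combining rule and no requirement to keep each setting

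*Combined protocol and SAP*

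**What the plan says.** **Who knows the lens.** Section 5.2 (Masking): "Investigators and clinical site personnel involved in the data collection will not be masked as to the identity of the investigational product". The subjects' own masking is acknowledged to be fragile, since "the dynamic nature of the test lens during the assessments may give the identity".

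**How a primary value arises.** Section 7.2, Psychometric Testing B, says for the two-point threshold: "An ascending and a descending method of limits will be used". For the starburst, "The investigator will adjust a calibrated custom-made micrometer", again in both directions and on subject feedback. The halo uses the same micrometer, and "Ascending and descending methods of limits will be used". The recording instruction for each test is a value per eye in mm to two decimals. No number of runs, combining rule or repeat rule is given, and nothing requires each run to be recorded.

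**Who calculates.** Section 15.1, introducing a list of the three primary and four secondary measures: "The follow data testing/measurements will be calculated and entered into the EDC at the study site".

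**What counts as source.** Section 15.2 allows the subject record to be the eCRF itself and takes the first point of entry as the source record.

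**What is analysed.** Section 14.5 models one threshold or diameter and does not say how it is formed from the settings. Test is declared better if the upper limit of the two-sided 95% interval for Test minus Control is below 0.

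**Odd values.** Section 14.9: "Missing or spurious values will not be imputed". Spurious is not defined, and no one is named to decide. The multiple-imputation sensitivity analysis depends on subject dropout above 15%.

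**The concern.** A method-of-limits threshold depends on which settings are taken, which are repeated and how they are reduced to one number. Here those choices fall to people who know the lens in each eye, and the plan fixes none of them. No misconduct is needed for bias. Repeating a setting that looks too large for the Test eye, or giving more weight to the run that seems cleaner, is ordinary judgement, and it can differ by lens when the lens is known.

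All six primary comparisons are exposed (three measures, each with the Test lens inactivated and activated). In each, a lower value favours Test, so the direction in which such judgement would help the product is plain to the operator. The contralateral design does not protect against this, because the selection acts on one eye of the pair and goes straight into the within-subject difference.

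**Working it through.** **Inputs from the documents.** 60 subjects targeted to complete (Section 14.2). A win needs the upper limit of a two-sided 95% interval below 0 (Section 14.5), which is a 2.5% false-win rate per comparison under no true difference. Section 14.2 says there is no power calculation and no historical data for the primary endpoints, so the plan has no figure to reproduce.

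**Assumptions.** Each eye has two settings, one ascending and one descending, with independent normal errors of equal SD. The endpoint should be their mean. The true lens difference is 0. Write *r* for the setting SD divided by the SD of the within-subject Test minus Control difference when means are used, and *q* for the share of subjects in whom the lower setting is kept for the Test eye only. A paired t test stands in for the mixed model. The documents give neither *r* nor *q*, so both are varied.

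**Step 1, shift in one eye.** The expected lower of two normal settings lies 1/√π = 0.564 setting SDs below their mean.

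**Step 2, bias in the lens difference.** Bias = 0.564 × *r* × *q*, in SDs of the paired difference.

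**Step 3, standardised shift.** Multiply by √60 = 7.746.

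**Step 4, false-win rate.** The normal approximation is Φ(shift − 1.96). The last column simulates the two settings directly and applies the paired t test (100,000 trials per row).

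| *r* | *q* | Bias | Shift | Normal approx. | Simulated |
|---|---|---|---|---|---|
| 0.2 | 25% | 0.028 | 0.219 | 4.1% | 4.1% |
| 0.2 | 50% | 0.056 | 0.437 | 6.4% | 6.2% |
| 0.2 | 100% | 0.113 | 0.874 | 13.9% | 13.6% |
| 0.5 | 25% | 0.071 | 0.546 | 7.9% | 7.7% |
| 0.5 | 50% | 0.141 | 1.093 | 19.3% | 18.3% |
| 0.5 | 100% | 0.282 | 2.185 | 58.9% | 55.5% |

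With *q* = 0 the simulation returns 2.5%, as it should. For scale, a bias of 2.001/√60 = 0.258 SD puts the average null result exactly at the significance limit.

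**Would the controls show it?** Set against the sequence of events:

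- A value changed or removed after entry would be seen by the audit trail and queries (Section 15.1) or the count of missing values (Section 14.9).
- A setting repeated or dropped before entry is not reached by these. Source verification (Section 17) compares the eCRF with source, but under Section 15.2 a calculated number typed straight into the eCRF is itself the source.

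**Recording load.** 3 tests × 2 lamp states × 2 eyes = 12 values per subject at Visit 2. With one setting in each direction, 12 × 2 = 24.

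**The case against.** Several points on the other side are fair.

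- **A reader might infer that the site enters only the final number.** The text does not say so. The eCRF specification is not among the documents, Section 15.1 says the forms are designed to match the study procedures, and equipment data not captured in EDC go to the sponsor. What stands is that nothing requires each setting to be entered or kept.
- **A reader might infer that selection would be undetectable.** That goes too far. Audit trails, queries, identifiable authors of entries, source access, monitoring and missing-value counts would show changes made after entry. What stands is the gap before first entry.
- **A reader might infer that site staff may discard values they consider spurious.** The sentence in Section 14.9 is a rule against imputation, in a section whose analyses are done by or for the sponsor. It gives the site no such power. The missing definition is a lack of detail, not the core of this point.
- **A reader might extend this to all seven endpoints.** Ascending and descending runs are described only for the three primary measures, and squint is taken from video that could be re-read.
- **The largest figures need selection in every subject.** That is so, which is why a range is shown. At *r* = 0.2 with selection in a quarter of subjects the effect is small.
- **Capturing settings does not mask the person turning the micrometer.** This also stands. Each run could still be set differently by lens. The fix closes one route of bias, and tester masking is a separate issue, on which the protocol is open.

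**Conclusion.** The point holds for the three primary measures. Unmasked staff take the settings and calculate the endpoint at the site, with no rule for combining or repeating settings and no duty to retain them. Because first entry is source, handling before entry may not be traceable. The documents do not show that selection will happen, and they do not show that it could never be found.

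As an illustration, the false-win rate per primary comparison rises from 2.5% to between about 4% and 14% at *r* = 0.2, and between about 8% and 56% at *r* = 0.5, as the share of subjects affected goes from a quarter to all. These figures rest on two settings per eye, independent normal errors, selection in the Test eye only, 60 completers and assumed SD ratios. With more settings per eye, dropping the least favourable one would move the mean less. The change is worth making because it is cheap and removes a route of bias that the analysis cannot correct afterwards.

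**What to change.** 1. **Section 15.1 and the Visit 2 recording steps in Section 7.2.** Require every ascending and descending setting, including repeats, to be entered by eye, lamp state and test. State the planned number of settings and when a repeat is allowed.
2. **Section 14.5.** Derive each primary endpoint at the sponsor by a prespecified program, for example as the mean of all settings.
3. **Section 14.9.** Say what makes a setting or value excludable and who decides. The reason should be recorded when the reading is taken, or the decision made masked to lens before database lock. The grounds should not be confined to instrument faults, since lost alignment or a lost or damaged lens can also spoil a reading.
4. **Reporting.** List each exclusion with its reason, by lens, and report the primary analysis with and without exclusions.

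The cost is at least 24 instead of 12 numbers per subject at Visit 2, an eCRF edit and one derivation program. The settings are already taken, so visit time should hardly change. The setting-level data would also give the within-eye variability useful for the follow-up sample sizes mentioned in Section 14.2.
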